Participants who meet inclusion/exclusion criteria will be randomized into a study condition and will be assigned to a project therapist. Because most VAMC patients who meet study criteria likely will present with multiple depressive/anxiety disorders (Brown et al., 2001), principal diagnosis, or the most impairing of the diagnosable disorders, will be used to inform randomization. Principal diagnosis will be determined via diagnostic severity scores in the Anxiety Disorders Interview Schedule-5 (ADIS-5) (Brown, 2014). To balance diagnoses across the two conditions, a stratified random assignment based on principal diagnosis will be used (MDD, PTSD, and PD/AG) ([name], 2015). Based on referrals to the PI's CDA, it is expected that at least 45% of the recruited Veterans will have served in OEF/OIF and $\geq 50\%$ will be representative of minority groups.

Eligible VAMC patients will be randomized into one of two treatment conditions: TBT or DSTs. Both treatment conditions will include 12 weekly 45- to 60-minute treatment sessions. Both treatment conditions will be delivered either in-person and via VA-approved telehealth technologies, based upon the preference of the participant. The general format of sessions will involve: 1) brief check-in; 2) review of materials from previous sessions; 3) review of homework assignments; 4) overview of new materials and in-session exercises; and 5) assignment of homework for next session. Attendance and homework completion will be recorded.

Randomization Procedures

Participants will be randomly assigned (1:1) to one of the two study arms ($n = 108$ per arm) using a permuted block randomization procedure. Randomization will be stratified by diagnostic group (PTSD, PD/AG, MDD) and block size will be varied to minimize the likelihood of unmasking. After determining eligibility and completing consent and baseline assessment materials, enrolled participants will be assigned to their treatment condition by the Research Project Therapist/Coordinator using a computer-generated randomization scheme. Once a participant is randomized, they will be included in the modified intent-to-treat (MITT) analysis. The Research Project Therapy/Coordinator and the statistical analyst in charge of randomization ([name]) will be the only

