The MITT analysis set will comprise all randomized participants. Missing data in the full analysis set will occur if participants discontinue treatment prior to the end of the study or do not complete an outcome measure. In general, participants will remain in the study unless consent is withdrawn or if there are concerns regarding participant safety. However, participants will be required to complete the full course of treatment (12 sessions) within a maximum of 18 weeks, in order to maintain the integrity of the treatments (Barlow et al., 2017). If participants fail to do so within 18 weeks, treatment will be discontinued and follow-up assessments will be completed. Missing data for the MITT analysis set will be accounted for using full information maximum likelihood (ML), which is superior to most alternative missing data approaches even when data is missing completely at random (MCAR) or missing at random (MAR; Schafer & Graham, 2002; Enders, 2010). Although the use of ML will result in the least biased parameters, regardless of data missingness, several approaches will be undertaken to better understand the exact mechanisms for missing data. Little's (1988) MCAR test will be applied to all final models to determine whether data can be considered MCAR. Further, the results of analyses using study completers and protocol adherers (completer and per-protocol analyses) will be compared with results using the MITT analysis set to test sensitivity of study conclusions to study discontinuations and protocol non-adherence. Baseline differences also will be explored between treatment completers and those that discontinue. If baseline differences are detected, these covariates will then be included in the final model as auxiliary variables to improve the plausibility of assuming data is MAR (Collins et al., 2001; Enders, 2010; Graham, 2003;). Finally, discontinuation proportion will be used as one of the outcome measures of intervention feasibility.

Efficacy Measures Analyses (Primary Aim)

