The continuous measures included measures of disorder severity scales (ADIS-5), disorder-specific symptomatology (PCL-5, PDSS, PHQ-9, and STICSA), general related symptomatology (STISCA), and quality of life and impairment (IIRS). Of these variables, the PCL-5, PDSS, PHQ-9, and STICSA are the primary outcomes of interest. All other analyses will be conducted in an exploratory fashion to inform future studies and compare findings to previous studies ([name], 2014; [name] et al., 2017; 2019). Parameter estimates to calculate the effect size difference will be arrived at using three-level (measurement occasions nested within participants nested within assigned treatment condition) generalized mixed-effects regression models (MRM). MRM is a method of repeated measures analyses that allows for modeling of continuous and categorical independent and dependent variables and for appropriate modeling of covariance structures when observations are correlated across time and/or across condition. This analytic approach fully captures variability in outcomes across multiple follow-up assessments and accounts for any potential effect of the group to which a participant is assigned and is thus preferred over methods that collapse data over time. We will calculate between-group treatment differences as Cohen's d, based on the effect of treatment condition on the intercept parameter when the model is centered on post-intervention and on the effect of treatment condition on the intercept parameter when the model is centered on month 6. We prespecified the non-inferiority margin (d) to be 0 (indicating we expected TBT to be at least equivalent to the aggregate DST effect) and the one-sided CI for our four primary analyses at $\alpha = .006$. In the primary analyses of outcome variables, we will covary for the baseline value of the variable of interest. We also will include the linear effect of time as well as a time by condition interaction effect to determine whether treatment differences (or lack thereof) were stable from post-intervention through the follow-up. Additional covariates (e.g. age, number of psychiatric comorbidities, race, sex, combat theatre, number of treatment sessions, specific DST received) will be added to the model to adjust for putative confounding variables. Effect size CIs that do not contain 0 provide evidence in support of noninferiority for TBT. The primary outcome time point is at the end of the active treatment phase and the secondary time point is at the end of the naturalistic 6-month follow-up period. Further, within-subject effect sizes from baseline to post-intervention and to 6-month follow-up also will be calculated within the TBT condition to quantify TBT-specific reductions in symptoms. These analyses will be probed to examine potential therapist effects. First, design effects will be calculated for the primary outcome variables. Design effects > 2 are often used as a heuristic to judge when these effects can be problematic.

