
Following testing of design effects, sensitivity analyses will be conducted using the complex estimator in Mplus which can adjust the model for potential therapist effects.

Feasibility and Acceptability Analyses (Secondary Aim)

Measures of feasibility and acceptability are discontinuation proportions (discontinuation y/n), proportion of sessions attended, proportion of homework assignments completed, and patient satisfaction scores on the STTS-R. Frequency distributions describing the participants' reasons for noncompliance and discontinuation of participation will be developed. Because feasibility and acceptability analyses involve changes from baseline to post-intervention only and several of the outcomes are categorical, the generalized linear mixed model (GLMM) framework will be used to compare TBT to DST on treatment satisfaction, retention (discontinuation), and treatment adherence (% missed sessions, % homework completion). Discontinuation proportions (dichotomous outcome), % of missed visits, and % homework completion will be compared between the intervention groups using GLMM, with logistic/binomial regression analyses as special cases for dichotomous and percentage outcomes; STTS-R will be modeled as a continuous outcome using an appropriate link function. We also will model the longitudinal profile of adherence as a dichotomous outcome at each visit (e.g. attended/did not attend a given session). This will allow us to evaluate the trends in session attendance and to determine if the trends differ by treatment (e.g. whether the probability of missing visits is less/greater at earlier or later time points).

E. PROTECTION OF HUMAN SUBJECTS

RISKS TO THE SUBJECTS

Risks to the Subjects

Participants will include 306 VAMC patients in the mental health service. The inclusion criteria are that participants must: 1) be an adult (18 – 80 years in age), 2) be competent to provide informed consent for research participation, and 3) be diagnosed with MDD, PTSD, and/or PD/AG as determined by a semi-structured diagnostic assessment (ADIS-5). Based on referrals to the Principal Investigator's ongoing CDA study, it is expected that at least 45% of the recruited Veterans will have served in OEF/OIF and $\geq 50\%$ will be representative of minority groups.

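### The primary efficacy model adjusts for number of treatment sessions, a post-randomisation variable, which can bias the TBT–DST comparison

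*Combined protocol and SAP*

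**What the plan says.** The paragraph under Efficacy Measures Analyses (Primary Aim) starts its model with "In the primary analyses of outcome variables, we will covary for the baseline value of the variable of interest". It adds linear time and a time-by-condition interaction, and then says that further covariates, given as an open list of examples, join the model: "number of treatment sessions, specific DST received) will be added to the model to adjust for putative confounding variables". The next sentence is the confidence-interval rule for non-inferiority. No primary model without the extra covariates is named.

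Other sections fix what session count is:

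- Procedures: "Both treatment conditions will include 12 weekly 45- to 60-minute treatment sessions".
- Missing Data, on completing the course in time: "If participants fail to do so within 18 weeks, treatment will be discontinued and follow-up assessments will be completed".
- Missing Data, on the analysis set: "The MITT analysis set will comprise all randomized participants".
- Feasibility and Acceptability Analyses (Secondary Aim): "Measures of feasibility and acceptability are discontinuation proportions (discontinuation y/n), proportion of sessions attended, proportion of homework assignments completed".

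On diagnosis, Randomization Procedures says: "Randomization will be stratified by diagnostic group (PTSD, PD/AG, MDD". The stratum is not itself listed among the model terms.

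**The concern.** With 12 sessions planned in both arms, the count differs between participants only through missed visits, discontinuation or the 18-week limit. All of these follow randomisation, and the assigned treatment may affect them. Such a variable cannot confound a randomised comparison. Conditioning on it changes the question from the effect of assignment in everyone randomised to a difference at equal attendance. Participants stopped at 18 weeks still have follow-up assessments, so people with short courses and observed outcomes do enter the model.

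The direction is not fixed. Suppose more sessions go with better outcome. If TBT is attended less, adjustment hides that disadvantage and makes false non-inferiority more likely. If TBT is attended more, adjustment removes benefit gained through attendance and costs power. The Secondary Aim hypothesis expects better attendance (defined there as weeks to completion) and better discontinuation rates with TBT; the second case applies if that carries over to session count. If early improvers stop early, both signs reverse. The Data and Safety Monitoring Plan offers alternative treatment to participants who worsen or do not improve. That is one possible route to a session–outcome relation, although it does not say that study therapy then stops.

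A smaller point concerns the term for the specific DST received, which has no defined value for TBT participants.

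**Working it through.** The plan gives no expected arm difference in sessions and no session–outcome slope, so there is no figure to reproduce.

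**Inputs from the documents.** Total sample 306, taken as 153 per arm at 1:1 (Randomization Procedures states 108 per arm; that figure was not used). One-sided alpha .006. Margin 0 in the analysis section, 0.5 in the sample size section. Assumed TBT advantage 0.3 SD. TBT pilot completion 12/15 = 80.0% and 21/29 = 72.4%.

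**Assumed inputs.** Baseline–outcome correlation 0.6. Sessions and outcome share a latent factor with loadings 0.6 and 0.5. Lower score is better. One post-treatment time point, least squares, complete data. The planned mixed model with maximum likelihood was not simulated.

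**Formula.** In a linear model the size of the shift in the arm coefficient is (slope of outcome on sessions within arm) × (TBT–DST difference in mean sessions). It is zero if either factor is zero.

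**Dropout-scale model.** Completers attend 12 sessions and others 1–7, mean 4, so each completion point is worth 0.08 session.

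| Completion | Session gap | Shift | False non-inferiority, TBT lower | Power, TBT higher |
|---|---|---|---|---|
| 80.0% v 72.4% | 8 × 0.076 = 0.6 | 0.04 SD | 1.6% | 68% |
| 82.5% v 70.0% | 8 × 0.125 = 1.0 | 0.06 SD | 3.2% | 57% |

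False non-inferiority is evaluated at the margin; power uses margin 0 and a true 0.3 advantage. Without the session term the figures are 0.5% and 78%. The pilot rates are both from TBT and serve only as an example of spread, since no DST rate is given. At the 1-session gap, weaker (0.3/0.3) and stronger (0.7/0.7) loadings give shifts of 0.02 and 0.10 SD, false non-inferiority of 1.0% and 8.0%, and power of 70% and 46%. With no session–outcome relation the shift is 0.00; with the relation reversed, its sign reverses.

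**Continuous-session model (SD 3, no ceiling).** This shows how the bias grows and can be checked by hand.

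- Slope = 0.6 × 0.5 / 3 = 0.10 SD per session.
- Residual variance = 1 − 0.6² = 0.64 without the term, and 0.64 − 0.30² = 0.55 with it.
- SE without the term = √(2 × 0.64/153) = 0.0915. Power = Φ(0.3/0.0915 − 2.512) = 78% (simulated 77%).
- SE with the term at equal attendance = √(2 × 0.55/153) = 0.0848. Power = 85% (simulated 84%).
- TBT +1 session: SE 0.0860, apparent advantage 0.3 − 0.1 = 0.2. Power = 43% (simulated 42%).
- TBT −1 session: false non-inferiority = Φ(0.1/0.0860 − 2.512) = 9% (simulated 9%).
- TBT −2 sessions: SE 0.0894. False non-inferiority = Φ(0.2/0.0894 − 2.512) = 39% (simulated 39%).

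**Margin 0.5, true difference 0, 1-session gap (dropout-scale model).** Power is 99.4% with the term and 99.9% without.

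**The DST term.** An intercept, an arm indicator and three DST indicators that are non-zero only in the DST arm have rank 4 for 5 columns. Dropping one DST indicator makes the arm coefficient TBT versus a single DST, not versus the aggregate. Diagnosis coded in both arms has full rank (4 of 4).

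**The case against.** Four arguments deserve weight.

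1. **Which model is meant.** The list is open, and it follows a sentence giving the primary model with baseline adjustment only. A secondary adjusted model may have been intended. That is possible, but the text does not say so, and the decision rule comes straight after the covariates. On either reading the plan needs a sentence.

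2. **Scale.** The largest figures need a 2-session gap, about 25 completion points at 0.08 session per point, against a pilot spread of 7.6 points. They also use uncapped sessions and fairly strong loadings. At 0.3/0.3 in the continuous model, false non-inferiority is 1.2% and 2.9% at −1 and −2 sessions, and power is 64% and 47% at +1 and +2. This stands, and the dropout-scale results are the better guide.

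3. **Missing outcomes.** The zero bias without the session term depends on complete data. With TBT one session lower in the dropout-scale model and half of non-completers' outcomes missing, the shift is −0.019 SD without the term and −0.058 with it (false non-inferiority 0.7% versus 2.3%). With three quarters missing it is −0.034 versus −0.056 (1.5% versus 2.6%). With all missing the two models coincide at −0.055 (2.4%). With TBT higher and half missing, power without the term is 64%, not 78%. So the benefit shrinks as missingness grows, but in these settings the model without the term is never the more biased one.

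4. **Margin.** The material power loss belongs to margin 0; at 0.5 it almost vanishes. This also stands. The two margins conflict, which is a separate issue.

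The DST objection is conditional too: if the term means the matched diagnosis in both arms, it is the stratum and does no harm.

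**Conclusion.** The concern holds. As written, the plan puts a post-randomisation feasibility outcome into the model used for the primary comparison and calls it a confounder. The resulting coefficient need not estimate the difference in all randomised participants. That conclusion follows from the design and needs none of the simulated figures.

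The size cannot be derived from the documents. At the pilot-scaled gap, the assumed model gives a modest shift that roughly triples a very small error rate or costs about 10 percentage points of power (78% to 68%) at margin 0. Larger attendance gaps or a stronger session–outcome relation make it serious. These figures rest on the assumed loadings, one time point and complete outcome data. The direction depends on which arm attends more and on the sign of the session–outcome relation. The matter should be fixed before analysis.

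**What to change.** In Efficacy Measures Analyses (Primary Aim):

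- Remove number of treatment sessions from the primary model.
- Replace the specific DST received with the randomisation stratum (principal diagnosis: PTSD, MDD, PD/AG), coded in both arms.
- Limit the remaining covariates to a named list of baseline variables.

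Label any session-count analysis as exploratory or sensitivity work beside the one already planned under Missing Data, where "the results of analyses using study completers and protocol adherers (completer and per-protocol analyses) will be compared with results using the MITT analysis set". Treat medication changes and non-study psychotherapy in the same way; Eligibility Criteria and Risks to the Subjects mention them as possible covariates without naming a model. DST-specific effects can go in a separate exploratory treatment-by-stratum model with centred coding.

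The change is to wording only, since principal diagnosis is already recorded for everyone at randomisation. The cost is the precision the session term would add if attendance were equal across arms and related to outcome: power of 81% versus 78% in the dropout-scale model, or 84% versus 77% in the continuous one. Equal attendance cannot be known in advance.

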For all study outcomes (ADIS-5, IIRS, PCL-5, PDSS, PHQ-9, and STICSA), Veterans will be randomly assigned (1:1) to the TBT and specific DST conditions. The power analysis was calculated to be powered at 80% with a Bonferroni-corrected 1-tailed $\alpha = .006$ (.025/4 primary outcomes) to detect non-inferiority for TBT in comparison to the aggregated DST effect. Meta-analyses for CBT for MDD, CPT for PTSD, and CBT for PD/AG reveal large treatment effects (CBT for MDD bias-adjusted $g = .53$; Cuijpers et al., 2013; CPT for PTSD in military personnel $g = 1.33$; CBT for PD $g = 0.35$; Hofmann & Smits, 2008). Thus, the average effect size for DSTs was expected to range from small-to-medium to large. A power analysis was conducted using procedures recommended by Chow, Shao, and Wang (2017), Flight and Julious (2014), and Julious (2004) as well as recommendations by the United States Food and Drug Administration and the European Medical Association (Food and Drug Administration, 2017). An important topic in non-inferiority designs is selection of the “appropriate” prespecified non-inferiority limit. Current best practice involves selecting a non-inferiority margin that is not greater than the smallest effect size expected for the DSTs in comparison to a control condition. As a tradeoff between sample size needs and feasibility of recruitment, we conducted power analysis setting the non-inferiority margin to 0.5, indicating that we would consider TBT non-inferior to the DSTs if TBT were to perform less than half a standard deviation worse than the DSTs. We set the expected group different to 0.3 given our pilot data demonstrating that TBT outperforms DSTs by this margin across primary outcome variables. Using procedures recommended by Chow, Shao, and Wang (2017) for non-inferiority designs, which utilize the pre-specified non-inferiority margin (here prespecified as $\Delta d = 0.5$) and the estimated effect in the active comparison treatment ($d = 0.3$), we determined that 144 participants (72 per cell) would be needed. However, this does not account for potential attrition or for potential design effect issues involving therapist effects or for potential missing data related to telehealth delivery of services. To account for possible attrition and missing data as well as the potential influence of design effects, we increased the sample size to 306 participants based on the data available to date. Based on pilot data, we expect to find large within-person effects ($d \geq .80$) for TBT, indicating 4/5ths of a SD reduction in each of the primary outcome measures. This sample size would leave us powered to detect small-to-medium within-person effect sizes.

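### The only therapist-adjusted analysis uses a sandwich estimator with no small-sample correction, so its interval is too narrow unless therapists are numerous, and their number is not stated

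*Combined protocol and SAP*

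**What the plan says.** The primary model, in Efficacy Measures Analyses (Primary Aim), has three levels: occasion, participant and treatment condition. Therapist is not one of them. The .006 level is attached to the primary analyses: "the one-sided CI for our four primary analyses at $\alpha = .006".

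Therapist effects come at the end of the same section. Design effects are calculated first, with a value above 2 mentioned as a rule of thumb. Then "sensitivity analyses will be conducted using the complex estimator in Mplus which can adjust the model for potential therapist effects". The plan gives no reference distribution, no small-sample correction, no minimum number of therapists, and no level or decision rule for this analysis.

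Procedures says that each participant is assigned to a project therapist. Neither the number of therapists nor the layout (crossed with arm or nested in it) is stated anywhere.

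**The concern.** A cluster-robust (sandwich) standard error is estimated from the variation between clusters, here therapists. With many clusters the normal approximation is good. With few, the variance estimate is biased low and itself very variable, so an interval built with a normal cutoff is too short. A level as small as .006 makes this worse, because normal and t tails differ most far out.

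The purpose of this analysis is to show whether the non-inferiority result survives allowance for therapists. If its interval is too short, a pass may reassure falsely, and no other planned analysis would reveal it.

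**Working it through.** **Inputs from the documents.** One-sided .006 per primary outcome, which is .025/4 = .00625 as printed; normal cutoff z(.994) = 2.512. Enrolment of 306, with the MITT set defined as all randomized participants. One VA medical center and its affiliated clinics. The plan gives no error rate for the therapist analysis, so there is no stated figure to reproduce.

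**Assumptions, because the documents are silent.** The complex estimator is a sandwich variance with a normal reference. Therapist count G runs from 4 to 30, in both layouts. Results are shown without and with a G/(G-1) variance factor. Where an intraclass correlation (ICC) is needed, .01 and .05 are used for illustration.

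**How many therapists?** "Both treatment conditions will include 12 weekly 45- to 60-minute treatment sessions". At most 306 × 12 = 3,672 sessions fall in months 6 to 45, which is 39 months or about 169 weeks. That is 3,672/169 = 21.7 sessions a week. A small team could carry this load, but it measures workload and not headcount.

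**Formulas (balanced caseloads, true difference on the decision boundary).**
- Crossed: the estimate is the mean of G within-therapist differences, and the uncorrected sandwich variance is (G-1)/G times the unbiased one. Error = P(t on G-1 df > 2.512 × √((G-1)/G)). For G = 8: 2.512 × √(7/8) = 2.350, giving .0255.
- Nested, k = G/2 therapists per arm: error = P(t on G-2 df > 2.512 × √((k-1)/k)). For G = 8: 2.512 × √(3/4) = 2.176, giving .0363.
- With the factor, multiply the cutoff by √(G/(G-1)).

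| G | Crossed | Crossed, with factor | Nested | Nested, with factor |
|---|---|---|---|---|
| 4 | .0589 | .0434 | .1088 | .0884 |
| 6 | .0352 | .0268 | .0548 | .0440 |
| 8 | .0255 | .0201 | .0363 | .0295 |
| 10 | .0205 | .0166 | .0274 | .0227 |
| 12 | .0175 | .0144 | .0224 | .0188 |
| 20 | .0121 | .0106 | .0142 | .0125 |
| 30 | .0098 | .0089 | .0110 | .0100 |

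Every entry exceeds .006. Simulation with unequal caseloads (306 participants, 8,000 runs per case, nested, with the factor, ICC 0 to .10) gave .09 to .11 at G = 4, .03 to .04 at G = 8 and .011 to .013 at G = 30. The excess is present at ICC = 0, so it comes from the estimator and not from an assumed therapist effect.

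**Comparison with the unadjusted primary test, crossed.** Simulation with a single post-treatment outcome, 306 participants, ICC .05, 20,000 runs, and arms allocated at random within therapist:
- G = 4: unadjusted .006, sandwich .059, therapist fixed effects .006.
- G = 8: unadjusted .0055, sandwich .026, therapist fixed effects .0055.

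If therapists' caseloads are split unevenly (alternately 70:30 and 30:70), the unadjusted test also drifts, to .023 at G = 4 and .013 at G = 8. The sandwich gives .070 and .026. Fixed effects stay at .006 and .005.

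**Comparison with the unadjusted primary test, nested.** Its error is P(Z > 2.512/√DE), with DE = 1 + (306/G - 1) × ICC. For G = 8 and ICC .05: DE = 1 + 37.25 × .05 = 2.86, and 2.512/1.692 = 1.485, giving .069.

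| G | Unadjusted, ICC .01 | Unadjusted, ICC .05 | Sandwich (no factor) |
|---|---|---|---|
| 4 | .029 | .125 | .109 |
| 8 | .016 | .069 | .036 |
| 12 | .012 | .046 | .022 |
| 20 | .009 | .0275 | .014 |

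At ICC .05 the unadjusted test is the worse of the two; at ICC .01 the sandwich is. Both exceed .006 throughout.

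**Width of a valid interval, nested.** The t critical value on G-2 df is 9.05, 3.55, 3.06, 2.79 and 2.69 for G = 4, 8, 12, 20 and 30, against 2.512. The sandwich interval with the factor has 23%, 65%, 78%, 88% and 92% of the valid half-width.

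**The case against.** Four points can be made for the plan.

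- **Few therapists are not established.** A reader might infer from the single site that the therapists are a handful and that the error must therefore reach .02 to .09. The documents do not support that step. Recruitment covers the medical center and all its affiliated clinics, sessions may be by telehealth, and four treatment protocols are staffed. At 20 to 30 therapists the error is about .01. This stands, and the sizes above are conditional on the count.
- **The check is not always easier to pass than the primary test.** A reader might infer that it is. That holds if therapists are crossed with arm and their caseloads are divided evenly or at random. If they are nested and therapists differ appreciably, the unadjusted primary test is itself too liberal and usually the worse of the two. This also stands.
- **No .006 test is attached to this analysis.** That level belongs to the four primary analyses, so applying it here is an assumption. A check on those analyses would naturally use their level, and an interval built this way is too short at other small levels too, but the trial's decision does not run through it.
- **Details of the estimator are assumed.** The normal reference and the variance factor are not in the documents. The factor lowers the error but does not bring it to .006 at any count tried.

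None of this makes an uncorrected sandwich valid with few clusters.

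**Conclusion.** The point holds in conditional form. With a normal reference and the .006 level, the therapist-adjusted analysis has actual one-sided error of about .02 to .06 with 4 to 10 crossed therapists, about .02 to .11 with 4 to 12 nested in arm, and about .01 with 20 to 30. Its interval was too narrow at every count tried.

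If therapists are crossed with arm, with caseloads divided evenly or at random, the check is easier to pass than the primary analysis, which then holds about .006. If they are nested and a therapist effect exists, both are too liberal, and which is worse depends on the ICC.

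A reader might infer that the primary conclusion is invalidated by this route. It is not, because this is a sensitivity analysis. It deserves correction because nothing else in the plan adjusts for therapist. The conflicting margins (0.5 in the sample-size section, 0 in the analysis section) are a separate matter and do not affect it: the error is evaluated at whichever boundary applies.

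**What to change.** Replace the estimator named at the end of Efficacy Measures Analyses (Primary Aim), and state whether therapists are crossed with or nested in arm.

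- **Crossed:** therapist fixed effects, or a therapist random intercept with Kenward-Roger or Satterthwaite degrees of freedom.
- **Nested:** fixed effects cannot be used, because therapist and arm are confounded. Use the random intercept with those degrees of freedom, or a CR2 (bias-corrected) sandwich with t degrees of freedom.

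Report the number of therapists and the participants per therapist by arm.

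The cost is a few lines of SAP text, standard software and a wider interval. With 20 or more therapists the widening is modest. With four nested in arm the critical value is 9.05 on 2 df against 2.51, about 3.6 times as large, and the analysis would say little. That limit comes from the design and should be known before the data are analysed.
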